The purpose of this study is to compare patient centered outcomes for those patients being treated for an uncomplicated VOC in ICs and EDs. We have designed this study based on preliminary, single site retrospective data on ICs from our participating sites which have shown similar outcomes to that of Benjamin²⁴. The Johns Hopkins Sickle Cell Infusion Center (SCIC) which opened in 2008 provides acute care solely for adults with SCD. In 2008, 50% of all ED visits for VOC resulted in hospital admission at Johns Hopkins Hospital (JHH). The SCIC initially was opened 5 days a week and in 2011 increased hours to include the weekends. The SCIC has 5 treatment slots for acute care visits, and is staffed by a clinic coordinator, nurse, clinical nurse associate, social worker and physician extender. Supervision is provided by [name], who is the medical director and the proposed PI for this study. From the period February 2008 through December 2011 there were 3874 visits to the SCIC by 361 unique patients. On average, there were 3.8 visits to the infusion clinic daily (range 0-10). The average number of visits by each individual was 10 (range 1-84) or 2.5/yr. Eighty five percent of visits ended with the patient being discharged home. The remainder were either directly admitted to the hospital or sent to the ED for further treatment. *The average time to receipt of first dose of opioid from arrival to the clinic was 57.7 minutes* (95% CI 56.5, 58.8). The average time that patients spent in the SCIC was 4 hours and 55 minutes. The average pain level on arrival using the numerical rating scale (NRS), which measures pain on a scale of 0-10, was 8.4 (95% CI 8.3, 8.4). The average decrease in pain score from arrival to discharge was 2.62 points on the NRS (95% CI 2.55, 2.69). Those who went home had a significantly greater decrease in pain than those that remained for hospital care (Δ -2.9 vs. Δ -1.2, $p<0.001$). There was borderline statistical but no clinically significant difference in time to first dose of opioid for patients who were discharged home compared to those that required additional hospital care (57.2 min v 60.3 min, $p=0.06$). In examining the association of changes in pain scores with discharge disposition, we found that, after adjusting for gender, patients were 2 times (OR 2.01, 95% CI 1.85, 2.19) more likely to be discharged home for every 1 point decrease in their pain. In comparing these outcomes to the JHH ED between 4/2010-7/2012, there were 1554 total ED visits for SCD pain made by 254 unique patients. *In the ED, the average time from triage to first dose of pain medication during this time period was 190 minutes* (SD 129.8). In a model controlling for acuity in the ED, for every 10 minute increase in time to first dose of pain medication, the relative risk of admission increased by 0.7% (95% CI 1.00 1.01, $p=0.024$). Since the opening of the SCIC there has been a 22% reduction in admissions and reduction in 30 day readmissions from 39% to 22%.

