After participants have consented they will be asked to contact by phone or email the research assistants about all acute care visits. In addition, the research assistant will review the daily census for IC's and ED's at the local site to identify participants with an acute care visit. Furthermore, each participant will be contacted by phone monthly and asked about acute care visits.

Once an acute care visit for an uncomplicated VOC has occurred, the following data will be collected: Time crisis started, Arrival time, Triage time, Pain level on arrival, Time to first dose of opioid, Time from first dose to nurse reassessment of pain, Time in the ED/IC, Pain level at discharge from ED/IC, Change in pain scale from arrival to discharge, Disposition at time of discharge from ED/IC (home, admit, etc.). In order to assess patient experiences of care in the acute setting, participants will be surveyed either toward the end of their acute visit or by phone within 72 hours of their visit. As reinforcement, at each monthly call, we will verify contact information and encourage participants to call us within 3 days of any acute visit. The survey tools that will be used include the Painful Crises Experiences of Care for SCD tool (PEPS); a survey of safety and a survey of patient satisfaction with ED pain management.

- b. Study duration and number of study visits required of research participants. Participants will be part of the study for 18 months. During which time there will be no in person study visits. There will be monthly phone calls and contact at the time of acute care visits.
- c. Blinding, including justification for blinding or not blinding the trial, if applicable. NA
- d. Justification of why participants will not receive routine care or will have current therapy stopped. NA
- e. Justification for inclusion of a placebo or non-treatment group. NA
- f. Definition of treatment failure or participant removal criteria. NA
- g. Description of what happens to participants receiving therapy when study ends or if a participant's participation in the study ends prematurely. NA

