All data collection will be done using RedCap. RedCap is a secure web based database tool that has multisite functionality. Each external site will enter their data into a single database. Each external site will only have access to their own data through the site. As the central coordinating site, Hopkins will have access to all of the data. When data collection is complete and records are finalized the data will undergo data lock. As all data will be entered into a common database merging of data will be done after data is exported from RedCap into Stata for further analysis. Merging of data will need to be done for combining the demographic data with data collected from each acute visit.

5. Inclusion/Exclusion Criteria

All individuals with confirmed SCD who live within 60 miles of the study center or who already receive regular care at the participating centers will be eligible for enrollment. The only exclusions will be patients who are pregnant, who have been stable on chronic transfusion therapy and have not had a painful episode within two years of enrollment (transfusions may prevent all acute painful events) and patients who are unwilling or unable to sign consent.

6. Drugs/ Substances/ Devices

- a. The rationale for choosing the drug and dose or for choosing the device to be used. NA
- b. Justification and safety information if FDA approved drugs will be administered for non-FDA approved indications or if doses or routes of administration or participant populations are changed. NA
- c. Justification and safety information if non-FDA approved drugs without an IND will be administered. NA

Date: _____
 Principal Investigator: _____
 Application Number: _____

7. Study Statistics

Primary and secondary outcome variables: This is an observational study from which we will draw inferences about outcomes of care attributable to the treatment setting. As we are not randomizing patients to ED care or to IC care, we must control for confounders in the relationship between site of care and outcomes. We note, however, that there may be regional differences that impact on outcomes: percentage of high utilizers in the region, duration IC has been functioning, and ED crowding. In our study, we have clustering of individual patients by regions (n=4). We will account for both known and unknown confounders at the level of the regions.

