Given the anticipated differences in patients who seek care in these settings, we propose using propensity score techniques to balance patient characteristics in the two treatment groups both within and across sites. We will use relatively new methods developed for use of propensity scores in the context of multilevel data.⁴² We look towards using propensity scores for achieving balance in the distributions of covariates to allow for a causal comparison. Our treatment assignment is at the individual level and we propose using appropriate propensity weighting methods to generate valid causal inferences, under the assumption of absence of unmeasured confounders.

For causal comparisons, we adopt the potential outcome framework for causal inference.⁴³ Under the standard stable unit treatment value assumption (SUTVA)⁴⁴, which states that the outcomes for each patient are unaffected by the treatment assignments of the other patients, each patient has two potential outcomes corresponding to the two treatments (ED or IC care), only one of which is observed for each patient. We believe the SUTVA assumption to be true in our setting. We aim to estimate the population average treatment effect, although we may also look at the *population average treatment effect on the treated (ATT)*, which we expect will be very similar.

Notation Let $k = 1, 2, \dots, K$ denote number of regions and $i=1, 2, \dots, n_k$ denote the number of participants in region k . Total sample size is $n = \sum_{k=1}^K n_k$. Each subject belongs to one of two groups, ED (control) or IC (treatment) care. Let Z_{ki} be the binary variable indicating whether the subject is in the treatment ($Z=1$) or control ($Z=0$) group. Also, let U_{ki} be a vector of subject-level covariates and V_k be a vector of region-level covariates, and $X_{ki} = (U_{ki}, V_k)$. For each subject, an outcome Y_{ki} is observed, which, in our study, can be continuous or binary. The propensity score is defined as $e(X_{ki}) = \Pr(Z_{ki}=1 | X_{ki})$.

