Fitting a Propensity Model Given the multi-region (clustered) data, we cannot use standard techniques for propensity score modeling but instead will use a *random effects model* that accounts for clustering. We have chosen this model because we are uncertain about all of the cluster-level covariates that might impact on treatment effect. The few that we hypothesize to be regional-level confounders, as described above, we will include in the model. The individual level covariates will include: SCD complications, self-reported number of acute care visits and hospitalizations in the prior 12 months, pain rating upon first arrival for care, distance from residence to site of care, and demographic variables. The random effects model to generate the propensity score is as follows:

$$\text{logit}(e_{ki}) = \delta_k + X_{ki} \beta \quad (1)$$

This model includes individual level covariates, as well as cluster-specific intercepts due to measured and unmeasured cluster-level covariates, and a prior distribution for cluster-level main effects, $\delta_k \sim N(0, \sigma_\delta^2)$. We expect that since we will have many patients within each region (cluster), we should not have any difficulty in fitting the random-effects model. The goodness of fit of this model will be checked by conventional diagnostics of covariate balance between the ED and IC treated patients, checking the overall and within-region balance of the weighted distribution of covariates in the two groups.

Estimating an Overall Treatment Effect We will then use the inverse of the propensity score, e_{ki} , generated from the random effects model described above, to *weight the outcomes* for each individual. This will allow us to draw valid inferences about the differences between groups. We propose using a non-parametric clustered-estimator as our inverse-probability-weighted estimator.

$$\hat{\pi} = \frac{\sum_{k=1}^K \hat{\pi}_k w_k}{\sum_k w_k} \quad (2)$$

Where $w_k = \sum_{i \in k} w_{ki}$, $w_{ki} = Z_{ki}/e_{ki} + (1-Z_{ki})/(1-e_{ki})$, and $\hat{\pi}_k$ is the inverse-propensity weighted treatment effect for the k -th region. This estimator accounts for clustering of the patients by region. The standard error of the estimate will be generated by bootstrapping.

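### ED crowding is adjusted for only as a regional constant, so crowding and arrival timing that vary from visit to visit are left out of the propensity model

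*Combined protocol and SAP*

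**What the plan says.** All references are to the combined protocol and SAP.

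- **Section 7, opening paragraph.** Three regional differences that may affect outcomes are listed: "percentage of high utilizers in the region, duration IC has been functioning, and ED crowding". The plan undertakes to account for known and unknown confounders at regional level, with four regions.
- **Section 7, Notation.** The plan lets "V_k be a vector of region-level covariates". The subscript is region only, so each region has one value.
- **Section 7, Fitting a Propensity Model.** On regional factors: "The few that we hypothesize to be regional-level confounders, as described above, we will include in the model". Eq 1 also has an intercept for each region. The individual-level covariates are SCD complications, acute visits and admissions in the previous year, pain at arrival, distance to the site and demographics.
- **Section 7, Estimating an Overall Treatment Effect.** Eq 2 is a weighted average of inverse-propensity-weighted effects, each computed inside one region.
- **Section 7, on causal assumptions.** "We believe the SUTVA assumption to be true in our setting". No argument is given.
- **Section 4a.** Arrival and triage times are recorded at each acute visit, and "the research assistant will review the daily census for" the local ICs and EDs to find participants.
- **Section 3.** The Milwaukee IC opens on weekdays only. For Baltimore, "The SCIC has 5 treatment slots for acute care visits", with a mean of 3.8 visits a day (range 0 to 10) and a mean stay of 4 h 55 min.

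**The concern.** ED crowding is named as something to control, but it enters in a form that cannot differ between an IC patient and an ED patient of the same region. Crowding changes by hour and day, and it bears most directly on the primary outcome, time from arrival to first parenteral dose. Timing can also determine setting: a weekend patient in Milwaukee cannot use the IC. A factor that affects both setting and waiting time is a confounder, and the plan's causal reading rests on there being no unmeasured ones. At stake is the size of the reported IC advantage in minutes, and how far it can be generalised when IC places are limited.

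**Working it through.** **1. What the region-level term can do.** With the covariates split into individual (U) and regional (V) parts, Eq 1 is

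logit(e_ki) = δ_k + V_k γ + U_ki β.

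For a given region, δ_k + V_k γ is a single number. Four regions allow four such numbers. An overall intercept plus the three named regional factors already uses 1 + 3 = 4, so the factors cannot be separated from the region intercepts. Eq 2 then compares IC with ED inside region k, where V_k is the same for everyone.

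The result is that between-region crowding differences are removed by the intercepts and the within-region contrast, with or without V_k. Within-region differences are untouched.

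**2. What the individual-level list can do.** Pain at arrival is already a visit-level covariate, so the model has room for others. Arrival hour, weekday, ED load and IC load are all absent.

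**3. Possible size of the bias.** The documents give no figure linking crowding to setting, so this is an illustration.

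Inputs from Section 3 (Baltimore): ED mean 190 min, SD 129.8; IC mean 57.7 min; gap 190 − 57.7 = 132.3 min. The ED clock starts at triage and the IC clock at arrival, and the periods differ, so the gap only sets the scale.

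Assumptions: correlation ρ of visit-level crowding with ED time of 0.2 to 0.4; change g in the log-odds of setting per SD of crowding of 0.25 to 1.0, with crowded times making IC care less likely; IC time unaffected by crowding.

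Simulation: four regions, 200,000 visits in all, Eq 2 with normalised weights, and fixed region intercepts standing in for the random ones.

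| ρ | g | Bias, region intercepts (min) | Bias, three V_k terms instead (min) | Bias, visit-level crowding added (min) |
|---|---|---|---|---|
| 0.2 | 0.25 | −3.40 | −3.40 | −0.17 |
| 0.2 | 0.5 | −6.20 | −6.20 | −0.13 |
| 0.2 | 1.0 | −10.45 | −10.45 | 0.17 |
| 0.4 | 0.25 | −6.44 | −6.44 | −0.01 |
| 0.4 | 0.5 | −12.73 | −12.73 | −0.37 |
| 0.4 | 1.0 | −20.99 | −20.99 | 0.46 |

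The two region-level columns are identical, as step 1 requires. With ρ = 0 the bias was within about 0.5 min of zero.

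Hand check of the first row: for small g and about half of visits in each setting, mean crowding among ED visits is raised by about g/2 = 0.125 SD. The bias is then about 0.2 × 129.8 × 0.125 = 3.2 min.

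As shares of the gap, 3.4/132.3 = 2.6% and 21.0/132.3 = 16%. If crowding sends patients to the IC instead, the sign reverses. Section 3 reports a 0.7% relative rise in ED admission risk per 10 minutes of delay, so 21 minutes corresponds to about 2.1 × 0.7% = 1.5%.

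**4. IC load and the no-interference assumption.** The plan's daily figure reproduces on weekdays: 3874 visits over 1021 weekdays (February 2008 to December 2011) = 3.79, against 3.8 stated. Counting every day of 2011 gives 3874/1126 = 3.44. Opening hours are not given; 8 to 12 h is assumed. Slot use = visits × 4.917 h / (5 × hours open):

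- 3.8 visits: 18.7/40 = 47% (8 h) to 18.7/60 = 31% (12 h).
- 10 visits: 49.2/40 = 123% (8 h) to 49.2/60 = 82% (12 h).

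Capacity could bind on peak days, but not on average.

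**The case against.** **The plan promised only regional control.** This is correct. Section 7 speaks of confounders at the level of the regions, and the intercepts deliver that. The redundant term does no harm; the gap lies in what is missing at visit level.

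**Confounding is not shown.** This also stands. No section says that crowding steers patients between settings. Crowding that only lengthens ED waits is part of the ED care being compared and should not be adjusted away. The Milwaukee weekday schedule does show that timing affects setting at one site, but not that it affects waiting time.

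**The sensitivity analyses already cover it.** In part. The hidden-bias analysis asks how strong an unmeasured confounder would have to be, and its examples are patient preference and local culture or climate. It does not replace a covariate that can be recorded. V_k might still matter in the propensity-quintile analysis if that pools regions.

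**Stronger readings.** A reader might infer that the plan's figures show IC and ED capacity to be shared, and so contradict the no-interference statement. They do not. They come from one site, give no ED capacity, shared staff or beds, or turn-aways, and mention only that some IC patients were sent on to the ED. A reader might also treat days with more than 5 visits as days when the IC was full (18% of days, with 33% of visits, if visits are Poisson with mean 3.8). Slots turn over, so those figures count days needing a second turn, not saturation.

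**Conclusion.** The point holds in a limited form. The region-level crowding term adds nothing beyond the region intercept, and the propensity model omits crowding and timing that vary by visit. This follows from the text and from Eq 1 and Eq 2 without further assumptions.

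The consequence is conditional. If crowding or timing also drives setting, the bias in time to first dose is about 3 to 21 minutes in either direction, on a gap of about 132 minutes. That rests on the assumed ranges for ρ and g and on one site's background data. It is unlikely to reverse the primary conclusion, but it could shift the reported effect by up to about 16%. The change is worth making; the omission does not invalidate the study.

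On interference, the assumption is unsupported and breaches on peak days are plausible, not demonstrated. Rewording it alters no estimate; it only limits what may be claimed.

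**What to change.** In Section 7, Fitting a Propensity Model, add these covariates for visits in both arms:

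- arrival hour and weekday, from the arrival data already collected;
- the number of patients in the local ED at or just before arrival, excluding the index patient.

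Do not use a same-day IC total that includes the index patient or later arrivals, because it partly encodes the treatment. For example, if setting were assigned 50:50 at random and other IC visits were Poisson with mean 2.8, the probability of IC care given a total of c would be c/(c + 2.8): 0 at c = 0 and 8/10.8 = 0.74 at c = 8, although load played no part. If IC load is used, count only other patients already present at arrival.

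Check overlap for times when an IC is closed, and state in advance how those visits are handled. Report the estimate without the new covariates as a sensitivity analysis. Either justify the no-interference assumption or replace the statement of belief, and say that the effect applies at observed IC occupancy.

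Cost: SAP wording, a little more data entry, and possibly reduced overlap. The census is already reviewed daily to find participants; that it also yields patient counts at a given time is an assumption to confirm. Such counts may be hard to recover later, so settle this before data collection. Hour and weekday need nothing new.

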
A similar clinic to the SCIC opened at Froedtert Hospital in Milwaukee (FASCC) in 2011. The FASCC clinic is open weekdays and serves the needs of 300 adults with SCD. The average length of stay in the clinic is 3 hours and 96.5% of visits end with the patient being discharged home. Since this clinic opened there has been a 38% decrease in admissions and a decrease in 30 day readmissions from 61 to 28%.

Without a direct comparison of ED to IC, many argue that there is something different about the patients that receive care in an ED versus those that seek care in an IC. Further, the recent expansion in ICs has been driven primarily by economic consideration (length of stay, readmissions), rather than by patient-centered outcomes, on which there is a lack of data. Demonstrating attainment of important clinical outcomes in ICs may increase their stability and viability. **With this proposal we will demonstrate that the improved outcomes seen in an IC v. the ED are not due to differences in the type of patients seen for care but rather in the processes of care for VOC in these two sites.**

4. Study Procedures

- a. Study design, including the sequence and timing of study procedures (distinguish research procedures from those that are part of routine care).

We will prospectively enroll patients that are seen in participating centers into a study cohort. We will then capture data from their acute visits. We will enroll participants from 4 sites: Baltimore, Cleveland, Milwaukee and Baton Rouge. When any participant is treated in either an ED or IC, data on clinical outcomes and patient experiences of care will be collected.

Baseline data collection will include: SCD genotypes and co-morbidities³⁵

- a. AVN
- b. Gall bladder disease
- c. Sickle chronic lung disease
- d. Leg ulcer
- e. Priapism (male)
- f. Renal failure
- g. Retinopathy
- h. Stroke

2. Self-reported number of acute care visits and hospitalizations in the prior 12 months
3. Daily chronic pain using the Numeric Rating scale (NRS).
4. Prior and current treatments, including:
 - a. hydroxyurea use
 - b. chronic transfusions
 - c. pain medications, (specific regimens used to treat chronic daily or intermittent pain)

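### The propensity model does not name five patient variables that the study collects at baseline, so the weighted ED–IC contrast may stay confounded by measured differences, chiefly for admission

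*Combined protocol and SAP*

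**What the plan says.** Section 7 (Study Statistics) calls the study observational, accepts that confounding between site of care and outcome must be controlled, and bases its causal reading on there being no unmeasured confounders. Under Fitting a Propensity Model the patient-level variables are given as "The individual level covariates will include: SCD complications, self-reported number of acute care visits and hospitalizations in the prior 12 months", then "pain rating upon first arrival for care, distance from residence to site of care, and demographic variables". Regional factors and a random intercept per region are added. Model adequacy is to be judged by "checking the overall and within-region balance of the weighted distribution of covariates in the two groups".

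Section 4, item a, sets out a longer baseline collection. It opens with "Baseline data collection will include: SCD genotypes and co-morbidities". It continues with prior-year utilization, a daily chronic pain rating, "hydroxyurea use", "chronic transfusions" and the medication used for chronic or intermittent pain.

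The Sensitivity analysis paragraphs of section 7 describe propensity quintiles, a fixed-effect propensity model, a possible doubly robust estimator and a hidden-bias analysis. None of them names a covariate beyond the list above. The closing paragraph of section 3 (Background) says the study will show that better IC outcomes come from processes of care and not from the type of patient seen.

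**The concern.** Inverse-probability weights balance what is put into the propensity model, and anything else only so far as it correlates with what is put in. The listed variables capture disease severity in part. Disease type, background pain and current treatment are further ways in which IC and ED patients could differ, and the plan itself expects the two groups to differ.

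If these variables influence both where a patient is treated and whether the patient is admitted, leaving them out biases the weighted admission difference. The direction cannot be told from the documents, since sicker patients might favor either setting. A critic who says that IC patients are simply different could then point to variables that were recorded but not used. The hidden-bias analysis would indicate how strong such a factor must be. It would not remove the bias, and its stated examples are patient preference and local culture.

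**Working it through.** **1. Collected against named.**

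| Baseline item (section 4, a) | Named in the propensity model (section 7)? |
|---|---|
| Eight co-morbidities | Yes, as SCD complications |
| Acute visits and hospitalizations, prior 12 months | Yes |
| Genotype | No; section 4 names it separately from the co-morbidities |
| "Daily chronic pain using the Numeric Rating scale (NRS") | No; pain on arrival is a different variable |
| Hydroxyurea | No |
| Chronic transfusion | No |
| "pain medications, (specific regimens used to treat chronic daily or intermittent pain") | No |

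Five collected variables are not named in the model or anywhere else in section 7. The transfusion exclusion in section 5 does not make that variable redundant: it removes only patients who are stable on transfusion and have had no painful episode in two years.

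**2. Yardstick.** The plan states no figure for confounding, so there is none to reproduce. Section 7a gives admission rates of 50% (ED) and 27% (IC) with 205 per arm. Ignoring clustering and weighting:

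SE = √[(0.50×0.50 + 0.27×0.73)/205] = √(0.4471/205) = 0.0467, or 4.7 points.

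**3. Approximate bias (assumed effects).** Treat the five variables as one standardized score, and let bZ and bY be its log-odds per SD on setting and on admission, net of the listed covariates. The score's mean then differs between settings by about bZ SD. One SD moves admission risk by about bY × mean p(1−p), where mean p(1−p) = 0.4471/2 = 0.2236. So bias ≈ bZ × bY × 0.2236. This was compared with 2,000 simulated trials of 410 participants, with four region intercepts, 14 covariates of the listed kind, and 8 columns for the five variables left out or added.

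| bZ / bY (assumed) | Formula, points | Simulated, omitted | Simulated, added | SE ratio, added to omitted |
|---|---|---|---|---|
| 0.2 / 0.2 | 0.04×0.2236 = 0.9 | 0.87 | 0.07 | 1.01 |
| 0.3 / 0.3 | 0.09×0.2236 = 2.0 | 1.86 | 0.00 | 1.01 |
| 0.2 / 0.4 | 0.08×0.2236 = 1.8 | 1.55 | −0.07 | 0.99 |

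The range 0.87–1.86 points is 0.19–0.40 of the SE (0.87/4.67 and 1.86/4.67) and 4%–8% of the planned 23 points.

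**4. Overlap with the listed covariates.** Those figures apply only to the part of the omitted variables that the listed covariates do not explain. If 0.2–0.3 were instead the total effect, and prior use, arrival pain and complications explained an assumed 30%–50% of it, a simpler large-sample check (0.83 and 1.87 points with nothing explained) falls to about 0.83×0.5 = 0.4 up to 1.87×0.7 = 1.3 points.

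**5. Dependence on the assumptions.** For a single binary factor, bias = residual imbalance × effect on admission. An imbalance of 10 points and an effect of 10 points give 1.0 point. At 30 and 30 the result is 9.0 points. The documents supply no prevalence or effect for any of the five, so neither corner can be preferred from them.

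**6. Primary outcome.** With the same 10–30 point imbalance and an assumed effect of 15–60 minutes, the shift is 1.5–18 minutes. The historical Baltimore gap in section 3 is 190 − 57.7 = 132.3 minutes (the first figure runs from triage, the second from arrival), so the shift is 1%–14% of it.

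**The case against.** The strongest reply is that the list is introduced as what the model will include, which does not rule out more. A reader might infer that the five variables are going to be dropped. The text does not show that; it shows only that no one is committed to using them. That still matters, because covariates chosen after the data are seen are open to challenge.

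Second, complications, prior-year use and arrival pain already stand in for severity. This is fair. It is why the figures above hold only as effects net of those covariates, and the true residual effect may be smaller.

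Third, the link to outcome is thin. Section 3 reports an odds ratio of discharge of 2.01 per point of pain reduction. A reader might take this as proof that chronic pain predicts admission. It concerns change in pain during the visit, after treatment has begun, so it is indirect support at most.

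Fourth, existing analyses help somewhat. The balance check refers to covariates without expressly limiting them to those in the model, though it names no wider set. The quintile analysis could reveal poor overlap overall, though not by region.

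A reader might also infer that arrival day or hour is a missing confounder, because section 3 describes the Milwaukee clinic as open on weekdays. The documents do not support that. It is one background sentence on one clinic, Baltimore's hours include weekends, nothing is given for Cleveland or Baton Rouge, and no outcome is reported by day. Where an IC is closed, moreover, balance on day cannot be reached by adding it to the model.

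**Conclusion.** The gap is real. Five collected baseline variables are absent from the stated propensity model and from every named sensitivity analysis, so the plan as written does not close off confounding by patient differences it will have measured. This is certain as to the wording and uncertain as to size.

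At an assumed net effect of 0.2–0.3 log-odds per SD on both setting and admission, the bias is about 0.9–1.9 points, or 0.2–0.4 of a 4.7-point SE. It is less if those effects are partly carried by the listed covariates, more under stronger assumptions, and zero if the variables do not affect both setting and admission. It is a benchmark and not an estimate.

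A reader might conclude that the primary comparison of time to first dose is in doubt. The documents do not support this: they connect none of the five variables to that outcome, and the assumed shifts are small beside the historical gap. The exposure is chiefly in the size of the admission difference and in the credibility of the claim about patient type. Severity: minor to moderate.

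**What to change.** In section 7, name genotype, daily chronic pain, hydroxyurea use, chronic transfusion and home pain regimen as propensity covariates, and include them in the overall and within-region balance checks. Fix a simple coding of the home regimen beforehand (for example daily long-acting opioid, intermittent opioid only, none), since free-form regimens cannot enter the model directly. Inspect the overlap of ED and IC propensity scores in each region.

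The change is to SAP wording; all five variables are already collected. It adds about eight parameters if genotype and regimen are categorical. In the simulation the effective sample size fell from about 362 to 338–349 of 410, and the SE ratio was 0.99–1.03; the upper end arose when the added variables predicted setting but not admission. With about 410/4 ≈ 102 participants per region, some within-region imbalance will occur by chance, so the plan should say in advance what degree of imbalance would prompt a change to the model.

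A sensitivity analysis limited to arrivals while the local IC was open is optional. It would need each clinic's opening hours and does not belong in the main model.
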